3.10.10	Clinical Laboratory Variables (Hematology, Chemistry)	50
3.10.11	Vital Signs and ECG	51
3.10.12	Pregnancy Test	51
3.10.13	Physical Examination	51
4	References	52
5	Description of Appendix Tables and Listings	53
5.1	Tables and Figures	53

5.2 Listings.....	58
6 Appendices	61
6.1 Appendix 1: SAS code for POX-MVA-002 Example	61

Table of Tables

Table 1	Trial Procedure Schedule – Group 1	18
Table 2	Trial Procedure Schedule – Group 2	21
Table 3	Lesion Data from POX-MVA-002 clinical trial	28
Table 4	Wald differences of log MLD values from POX-MVA-002 clinical trial	31
Table 5	Sample size calculations for the Efficacy Endpoint	34

Table of Figures

Figure 1	Histogram of MLD from POX-MVA-002	30
-----------------	--	-----------

List of Abbreviations

AAR	Area Attenuation Ratio
ACV	Assay Cut-off Value
AE	Adverse Event
AESI	Adverse Event of Special Interest
ALT	Alanine Aminotransferase
AST	Aspartate Aminotransferase
ATC	Anatomical-Therapeutical-Chemical
BMI	Body Mass Index
BN	Bavarian Nordic
CBC	Complete Blood Count
CI	Confidence Interval
CTP	Clinical Trial Protocol
DAR	Diameter Attenuation Ratio
DRM	Data Review Meeting
DSMB	Data Safety Monitoring Board
ECG	Electrocardiogram
eCRF	electronic Case Report Form
ELISA	Enzyme-linked Immunosorbent Assay
FAS	Full Analysis Set
FU	Follow-up
GMT	Geometric Mean Titer
HL	Hodges-Lehmann
IMLD	Investigator Measured MLD
ISS	Initially Seronegative Subset
ITRC	Independent Take Review Committee
LCL	Lower Confidence Limit
MedDRA	Medical Dictionary for Regulatory Activities
MLA	Maximum Lesion Area
MLD	Maximum Lesion Diameter
MMLD	Memory aid MLD
MVA-BN [®]	Modified Vaccinia Ankara – Bavarian Nordic
PB	Price-Bonett
PPS	Per Protocol Set
PRNT	Plaque Reduction Neutralization Test
SAE	Serious Adverse Event
SAP	Statistical Analysis Plan
SAS	Statistical Analysis Systems
s.c.	Subcutaneous
SCR	Screening Visit
SD	Standard Deviation
SMLD	SilhouetteConnect camera system MLD
SOC	System Organ Class
SOP	Standard Operating Procedure

TCID ₅₀	Tissue Culture Infectious Dose 50%
V	Visit
WHO-DD	World Health Organization Drug Dictionary

Statistical Analysis Plan

This Statistical Analysis Plan (SAP) outlines the contents and methods to be used for the statistical analysis of the data collected during clinical trial POX-MVA-006 (FY12-19, HP-12-19) for all subjects. Prior to database lock a final version of the SAP will be produced.

This document is intended to provide additional information to the Clinical Trial Protocol (CTP). In case of a revision of the CTP the SAP will only be amended if there is a direct impact on the SAP.

Changes from Edition 7.0 to 8.0 of the SAP: the Hodges-Lehmann (HL) method of calculating the confidence interval of the ratio of the Maximum Lesion Area (MLA) medians replaces the Price-Bonett (PB) method in the analysis of the MLA-specific primary endpoint. The PB based calculation method will nevertheless be used for supportive secondary analysis of the MLA endpoint.

General Definitions

Full Take:

A full take is a successful primary take according to Vaccinia (Smallpox) Vaccine Recommendations of the Advisory Committee on Immunization Practices (ACIP) ([Morbidity and Mortality Weekly Report \[MMWR\] June 22, 2001](#)).

Formation of a major cutaneous reaction at the ACAM2000[®] vaccination site:

- The inoculation site becomes reddened and pruritic three to four days after vaccination.
- A vesicle surrounded by a red areola then forms, which becomes umbilicated (collapsed center) and then pustular by days seven to eleven after vaccination.
- The pustule begins to dry; the redness subsides; and the lesion becomes crusted between the second and third week, the scab falls off, leaving a permanent scar that at first is pink in color but eventually becomes flesh colored.

Partial Take:

After revaccination, skin reactions at the ACAM2000[®] vaccination site might be less pronounced with more rapid progression and healing than those after primary vaccination. Revaccination is successful if a pustular lesion or area of definite induration or congestion surrounding a central lesion (i.e. scab or ulcer) appears six to eight days after re-vaccination. A partial take is a successful primary take.

The above definitions of Take are according to Vaccinia (Smallpox) Vaccine Recommendations of the Advisory Committee on Immunization Practices (ACIP) ([Morbidity and Mortality Weekly Report \[MMWR\] June 22, 2001](#)).

Absent Take:

An absent take is considered to be the absence of a cutaneous reaction i.e. consistent with a full or partial take, at the ACAM2000[®] vaccination site.

Attenuation:

After revaccination, skin reactions at the ACAM2000[®] vaccination site are often less pronounced and there is more rapid progression and healing than those after primary vaccination. For the purposes of this SAP and corresponding CTP attenuation is considered to be when the takes observed in Group 1 subjects (MVA-BN[®] recipients vaccinated with ACAM2000[®]) are determined to be diminished full takes based on the median of the individually measured parameter of Maximum Lesion Areas in Group 1 subjects, in comparison to the median of Maximum Lesion Areas of takes in Group 2 subjects (ACAM2000[®] recipients).

Peak Visit:

For the purposes of this SAP, the Peak Visit is the visit with the highest expected antibody titers. For MVA-BN[®] the peak responses are considered to be at Day 42 after the first MVA-BN[®] vaccination (as described in the MVA-BN[®] Investigator's Brochure) when the subject has received two (2) MVA-BN[®] vaccinations according to the standard vaccination schedule. For ACAM2000[®] the peak responses are considered to be at Day 28 post vaccination in order to be in alignment with published data for conventional smallpox vaccines reaching a peak four weeks post vaccination (Frey, 2003; Belshe, 2004; Kennedy, 2004; Frey, 2007), which is also in full agreement with the data published for ACAM2000[®] (ACAM2000 Vaccines and Related Biological Products Advisory Committee [VRBPAC] Briefing Document, April 2007).

Individual Peak Titer:

For each subject in Group 1 the individual maximum Enzyme-linked Immunosorbent Assay (ELISA) titer from Visit 1 to Visit 7 will be used as the individual peak ELISA titer, and in Group 2 the individual maximum ELISA titer from Visit 1 to Visit 6 will be used. The individual peak Plaque Reduction Neutralization Test (PRNT) titer is then defined in the same way. Here it should be noted that although the visit numbering is a little different between groups the serum sample are taken at the same time points for Group 1 and Group 2 (no sample is taken at Visit 5 in Group 1).

Enrolled Subjects:

Subjects are considered enrolled once they have received the first trial vaccination. For this trial a vaccination means administration of either MVA-BN[®] and/or ACAM2000[®].

Trial Day:

The day of trial is calculated from the day of the first vaccination. The day of first vaccination is defined as Day 0 and the day after first vaccination is Day 1, and so on. Equally, the day before

first vaccination is defined as Day -1, and so on. In particular, no reference is made to the time of the vaccination in the calculation of the trial day, i.e. at midnight a new trial day begins regardless of the time of first vaccination. Note that it is possible for some Visit 1 procedures to be performed, for example, on trial Day -1 prior to vaccination at Day 0.

Baseline:

If not otherwise specified, 'Baseline' refers to the last measurement before first vaccination of trial drug. This is either at Visit 1 or Screening (SCR), or latest re-screening as appropriate. If there is missing vital sign data at Visit 1 then the Screening Visit or latest re-screening data will be used to impute the missing data. These data will be summarized as Baseline data without direct specification of which visit was used. However, at all other visits no imputation will be used and the actual visit used will be specified in tables or listings.

Screening Phase:

The screening phase is defined from the Screening Visit up to Visit 1 before the first vaccination. This includes any re-screening visits that are conducted.

Active Trial Phase:

All data collected from the first vaccination at Visit 1 up to (and including) either Visit 10 for Group 1 or Visit 4 for Group 2, or trial early termination visit. This could include any unscheduled visits up until Visit 10 or Visit 4, as appropriate.

FU Trial Phase:

The follow-up period begins immediately after the active trial phase and continues until the (remote) FU (Follow-up) Visit.

All data collected after Visit 10 for Group 1 and Visit 4 for Group 2 until, and including, the remote FU Visit (and if performed on-site FU Visit). Note that for some subjects for whom the remote FU Visit was not performed there may not be any FU phase data available, however this will not be considered a protocol deviation.

Eligible Subjects:

A subject is eligible if the question "is the subject eligible for the trial?" is answered with "yes" and there are no subsequent major protocol deviations that affect the eligibility of the subject.

Subjects Receiving Vaccinations:

A subject received trial vaccination according to the randomized group assignment if a date of drug administration is given for the vaccination and no major vaccine handling deviation is recorded on the electronic Case Report Form (eCRF).

Treatment Emergent Adverse Event:

An adverse event (AE) with onset either on the day of a vaccination, but after the vaccination, or within the 28 days following a vaccination.

Causally Related Adverse Event:

An AE with either a ‘possible’, ‘probable’, ‘definite’, ‘unknown’ or ‘not evaluable’ or missing relationship to the vaccine.

An adverse event with missing relationship and onset before the first vaccination will not be assumed to be causally related.

Adverse Drug Reaction:

A causally related treatment emergent AE.

Serious Adverse Event:

All Serious Adverse Events (SAE) recorded with onset after the first trial vaccination and before the end of the FU phase are considered as treatment emergent regardless of the day of onset.

Adverse Events of Special Interest:

Any Adverse Event of Special Interest (AESI) which is also classified as serious will be included in the analysis of SAEs and will not be included in the analysis of AESIs. All AESIs recorded with onset after the first trial vaccination and before the end of the FU phase are considered as treatment emergent regardless of the day of onset.

Assay Cut-off Value:

The Assay Cut-off value (ACV) for the vaccinia-specific ELISA can be found in SOP BN0002809: “Automated ELISA for Detection of Vaccinia Specific Antibodies in Human Sera”, and for the vaccinia-specific PRNT can be found in SOP BN0003536: “Human Plaque Reduction Neutralization Test Using Vaccinia Virus Western Reserve”.

The Geometric Mean Titer:

The Geometric Mean Titer (GMT) is calculated by taking the antilogarithm of the mean of the \log_{10} transformed titers. Antibody titers below the ACV will be given an arbitrary value of one for the purpose of this calculation.

Seronegative and Seropositive Result:

A seronegative result is a titer below the ACV, while a seropositive result is a titer equal to or above the ACV.

Seroconversion:

Seroconversion is defined at each post baseline visit as either the appearance of antibody titers \geq ACV for initially seronegative subjects or a doubling or more of the antibody titer compared to baseline titer at Visit 1 for initially seropositive subjects. Seroconversion is not calculated if either the Visit 1 or respective post baseline visit titers are missing.

Maximum Lesion Area:

The Maximum Lesion Area (MLA) is defined as the maximum of two measurements: the lesion area measured on Day 6-8 (after scarification) or the lesion area measured on Day 13-15 (after scarification).

There is only one lesion area measurement performed using the SilhouetteConnect camera system.

If one of the lesion areas is missing, then the MLA will be calculated as the single lesion area which is present. However, subjects with only one lesion area recorded will be considered a major protocol violation and will be excluded from the per protocol set (and therefore also from the initially seronegative set).

The MLA will be used in the co-primary endpoint analysis. However, the Day 6-8 and Day 13-15 lesion areas will also be reported and included as descriptive secondary endpoints.

Maximum Lesion Diameter:

The Maximum Lesion Diameter (MLD) is the largest major diameter measured across the lesion on Day 6-8 (after scarification) or Day 13-15 (after scarification).

There are three separate measurements of the MLD

- The SilhouetteConnect camera system MLD (SMLD) recorded on Day 6-8 (after scarification) or Day 13-15 (after scarification)
- The Investigator Measured MLD (IMLD) recorded on Day 6-8 (after scarification) or Day 13-15 (after scarification)
- The Memory aid MLD (MMLD) recorded by the subject on each day after scarification.

The Investigator maximum diameter, Day 6-8 diameter and Day 13-15 diameters will be used as supportive secondary analyses.

Lesion:

Lesion measurements (area and diameter) referred to in this SAP will include signs (after scarification) of pustule, vesicle, pus, ulcer or scab but will not include extended symptoms of induration or erythema.

1 Trial Overview

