### **7.3 Measurement of the Take**

A digital photograph will be taken of the vaccination site at the visits 6-8 days and 13-15 days after scarification with ACAM2000®.

The system for capturing the digital photographs and measuring the area of the lesion is described in detail in the ITRC Charter.

The ITRC will confirm the correct measurement of the lesion area by reviewing blinded subject profiles (as described in the ITRC Charter). Statistical calculations for attenuation of take will be based on the ITRC confirmed lesion areas.

The healing will be confirmed by the investigator at the appropriate scheduled visit.

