1.1 Trial Description

This is a randomized, open-label Phase III non-inferiority trial to compare indicators of efficacy for MVA-BN[®] smallpox vaccine to ACAM2000[®] in 18-42 year old healthy vaccinia-naïve subjects.

A total of 440 vaccinia-naive subjects will be assigned randomly to two parallel treatment groups in a 1:1 ratio, 220 subjects in Group 1 and 220 subjects in Group 2.

Group 1:

One 0.5 ml standard dose MVA-BN[®] liquid-frozen vaccine contains a nominal titer of 1×10^8 tissue culture infectious dose 50% (TCID₅₀) Modified Vaccinia Ankara – Bavarian Nordic (MVA-BN[®]).

Two vaccinations each of 0.5 ml MVA-BN[®] vaccine will be administered four weeks apart (Day 0 and Day 28) as a subcutaneous (s.c.) injection in the non-dominant upper arm, followed by a single vaccination of ACAM2000[®] administered four weeks after the second MVA-BN[®] vaccination (Day 56). As per the prescribing information: one dose of reconstituted ACAM2000[®] vaccine consists of $2.5\text{-}12.5 \times 10^5$ plaque forming units of live vaccinia virus. A droplet (~ 0.0025 ml) vaccine is picked up with a bifurcated needle and is administered by the percutaneous route (scarification) using 15 jabs of the bifurcated needle.

Group 2:

A single vaccination of ACAM2000[®] will be administered at Day 0.

The active phase of the trial will begin at Day 0 (Visit 1) and continue through the second MVA-BN[®] vaccination (Day 56) and until 28 days after the ACAM2000[®] vaccination of Group 1 subjects (Visit 10). The active phase of the trial will begin at Day 0 (Visit 1) and continue until 28 days after the ACAM2000[®] vaccination of Group 2 subjects (Visit 4).

A remote Follow-up (FU) Visit by telephone or email is planned six months after the last trial vaccination. Only if there is a medical need, will the subject be asked to come back to the site or at the FU Visit (and specifically in the case of deployed military subjects) at another medical unit as agreed upon by the Principle Investigator.

The total duration (including screening period) is up to 22 weeks for Group 1 and up to 18 weeks for Group 2, plus remote correspondence (e.g. a phone call or email) six months after the last vaccination. If the remote correspondence reveals a medical need or any underlying condition that requires further examinations, the subject will be called in for a physical visit.

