3.9.3 Immunogenicity and Efficacy Variables

Seropositivity (yes/no) at all sampling visits

- Vaccinia-specific neutralizing antibodies (PRNT)
- Total vaccinia-specific antibodies (ELISA)

Seroconversion (yes/no) at all post baseline sampling visits

- Vaccinia-specific neutralizing antibodies (PRNT)
- Total vaccinia-specific antibodies (ELISA)

Antibody titers at all sampling visits

- Vaccinia-specific neutralizing antibodies (PRNT)
- Total vaccinia-specific antibodies (ELISA)

The following assessments will be made using the SilhouetteConnect camera system (using the area perimeter drawn on the photograph)

- Lesion area at Day 6-8
- Lesion area at Day 13-15
- Lesion diameter at Day 6-8
- Lesion diameter at Day 13-15

The lesion area measurements will be confirmed by the blinded ITRC. Where there is a discrepancy, then the ITRC would have the final decision.

The following assessments will be made by the investigator

- Lesion diameter at Day 6-8
- Lesion diameter at Day 13-15
- Healing of lesion assessed at visits on Day 7, Day 14 and Day 28.

- Major erythema at Day 6-8
- Major erythema at Day 13-15
- Major induration at Day 6-8
- Major induration at Day 13-15

The following assessment will be made by the blinded ITRC:

- ITRC classification of lesion site (full take, partial take, absent take)
- MLA

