3.10.8 Efficacy Analysis

The co-primary efficacy endpoint of the trial is the MLA in mm^2 after scarification with ACAM2000. The primary analysis assesses if the AAR (based on the MLA) is significantly above $\lambda=40\%$ using the HL method for calculating the non-parametric confidence interval as described in [Section 3.3](#) and implemented using the HL option in the SAS procedure NPAR1WAY.

In addition, the median for each group (and overall for both groups) will be calculated along with the 95% non-parametric confidence intervals for the median ([Hahn, 1991](#)). This will be obtained using the SAS Univariate procedure with the option CIPCTLDF. In addition, the minimum and maximum values will be displayed.

A similar secondary supportive analysis will be performed using the PB method (described in [Appendix 6.1](#)). A similar secondary descriptive analysis will also be performed to calculate the confidence interval of the AAR (based on the MLD) using the HL method for:

- lesion area (mm²) at Day 6-8
- lesion area (mm²) at Day 13-15

and the DAR using the investigator measurements of:

- maximum lesion diameter (mm)
- lesion diameter (mm) at Day 6-8
- lesion diameter (mm) at Day 13-15

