16.2.1.5 Compliance

- 16.2.1.5.1 Dates of Visits and Blood Sampling – FAS
- 16.2.1.5.2 Investigational Product Administration – FAS

- 16.2.1.5.3 Memory Aid Accounting – FAS

Section 16.2.2 Efficacy and Immunogenicity

- 16.2.2.1 Measurement of Lesion Area and Diameter using the SilhouetteConnect camera system – FAS
- 16.2.2.2 ITRC Assessment of lesion following vaccination with ACAM2000® – FAS
- 16.2.2.3 Vaccinia-Specific PRNT Antibody Analysis: Titers, Seropositivity and Seroconversion Status – FAS
- 16.2.2.4 Vaccinia-Specific ELISA Antibody Analysis: Titers, Seropositivity and Seroconversion Status – FAS

Section 16.2.3 Safety

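### The diameter attenuation analyses rest only on the open-label investigator's measurement, while a camera diameter is collected but merely listed

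*SAP*

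**What the plan says.** SAP 1.1 describes the design: "This is a randomized, open-label Phase III non-inferiority trial to compare indicators of efficacy". Under Maximum Lesion Diameter, the SAP's General Definitions list three sources of the measurement: the SilhouetteConnect camera (SMLD), the investigator (IMLD) and the subject's memory aid (MMLD). They then assign one to the supportive analyses: "The Investigator maximum diameter, Day 6-8 diameter and Day 13-15 diameters will be used as supportive secondary analyses". SAP 3.10.8 repeats the choice, "and the DAR using the investigator measurements of", for the maximum, Day 6-8 and Day 13-15 diameters. Tables 15.2.1.2.1 to 15.2.1.2.3 report the investigator diameter only, and the camera Tables 15.2.1.1.1 to 15.2.1.1.3 report area only.

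SAP 3.9.3 takes both area and diameter at the two time points from the outline traced on the photograph. In the planned output the camera diameter appears only in Listing 16.2.2.1, "Measurement of Lesion Area and Diameter using the SilhouetteConnect camera system". For the area, SAP 3.9.3 adds: "The lesion area measurements will be confirmed by the blinded ITRC". Protocol 7.3 says likewise: "The ITRC will confirm the correct measurement of the lesion area by reviewing blinded subject profiles". Neither document plans a DAR from the camera diameter or a comparison of the camera and investigator readings.

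**The concern.** Under Protocol 7.4 the lesion is measured by the investigator or a designee, and nothing blinds that person. Group 1 is read at Visits 8 and 9 and Group 2 at Visits 2 and 3, so the visit number alone identifies the group. A reader who expects smaller lesions after priming could read them small without intending to. The memory-aid diameter, summarised by group under SAP 3.10.9, does not fill the gap, because subjects also know what they received.

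The plan protects the area endpoint through blinded ITRC review but gives the diameter no comparable protection, although a better-protected measure of the same quantity is collected. At stake is how much weight the diameter result can bear when it is reported beside the MLA. If it agrees with the MLA, the planned output gives no way to tell how much of the agreement comes from the lesion and how much from the reader's expectation.

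**Working it through.** **Inputs.** POX-MVA-002 diameters from SAP 3.3.4, Table 3: 12 primed subjects (median 7 mm) and 13 unprimed subjects (median 12 mm). Method from SAP 3.3.1: HL shift on log10 of max(1, MLD), with the interval taken from the ranked pairwise differences.

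**Reproducing the SAP's example.**
- DAR from medians: 1 − 7/12 = 0.417.
- E[U] = 12 × 13/2 = 78 and V[U] = 12 × 13 × 26/12 = 338, so the half-width is 1.96 × √338 = 36.03. Rounding up 41.97 and 114.03 gives ranks 42 and 115 of 156.
- HL estimate: the middle difference is −0.331, which is log10(7/15), so 1 − 7/15 = 0.533.
- Lower limit: the 115th difference is −0.155, which is log10(7/10), so 1 − 0.7 = 0.300.
- Upper limit: the 42nd difference is −0.628, which is log10(4/17), so 1 − 4/17 = 0.765.

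These match SAP 3.3.4 exactly.

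**Sensitivity to an assumed reading bias.** Non-zero Group 1 lesions are read b mm too small, zeros stay at zero, and Group 2 is read correctly. The direction and size of b are assumptions; the documents give no figure for either.

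| b (mm) | DAR from medians | HL 95% lower limit |
|---|---|---|
| 0 | 0.417 | 0.300 |
| 0.5 | 1 − 6.5/12 = 0.458 | 0.350 |
| 1 | 1 − 6/12 = 0.500 | 0.400 |
| 1.5 | 1 − 5.5/12 = 0.542 | 0.450 |
| 2 | 1 − 5/12 = 0.583 | 0.500 |

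**At the planned size.** The same diameters were resampled to 175 per group, with the uniform half-millimetre jitter of SAP 3.6.2 (3,000 resamples). With no bias the median HL lower limit of the DAR is 0.485. With 1 mm under-reading in Group 1 it is 0.560, a shift of 0.075. A larger sample narrows the interval but does not remove a systematic reading difference.

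**What cannot be computed.** The DAR from the camera diameter itself, because the documents contain no camera diameters.

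**The case against.** The strongest reply is that the SAP does what the protocol asks. Protocol 9.3.2 names the investigator-assessed diameter as a secondary endpoint, SAP 3.5 keeps it for comparison with historical practice, and Protocol 9.6 treats all secondary tests as descriptive. Other supportive analyses avoid the investigator's diameter: Price-Bonett on the MLA, camera areas at each time point, and the blinded ITRC classification of takes. All of this stands. It limits the weight of the point and argues for keeping the investigator endpoint.

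A second reply is that the camera diameter may be no better. Blinded confirmation is stated for the area, not the diameter, and neither document says who draws the perimeter. Protocol 7.3 leaves the details of the camera system to the ITRC Charter. The camera diameter also shares its perimeter with the MLA, so any tracing error is common to both, whereas the investigator's reading is a separate measurement. This stands too. A reader might infer that the camera diameter should replace the investigator's as an ITRC-confirmed measure; the documents do not support that.

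A third reply is that both diameters are listed by subject (Listings 16.2.2.1 and 16.2.3.1.4.1), so agreement could be examined later. It could, but a comparison by group specified before database lock is more credible than one assembled from listings afterwards.

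**Conclusion.** The point holds as a cheap improvement. The DAR analyses use only an unblinded reading, and a second measure taken from the ITRC-reviewed image is collected but not analysed. The bias is a risk, not a finding. Under an assumed 1 mm under-reading in Group 1, the SAP's example DAR rises by 0.083 (0.417 to 0.500) and its lower limit by 0.100 (0.300 to 0.400). The co-primary MLA and the camera-area analyses do not change.

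A reader might go further and infer that reading bias could turn a failure against 0.40 into a pass. The documents do not support this, for three reasons.
- The 0.40 in SAP 3.3.2 and 3.3.3 is a threshold for area. For circular lesions its diameter equivalent is 1 − √0.6 = 0.225, which the unbiased lower limit of 0.300 already exceeds.
- SAP 3.5 and 3.10.8 set no pass/fail rule for the DAR. SAP 3.3.4 does compare the example with 0.4, but it attributes the miss to the use of diameters and the small sample.
- At 175 per group with no bias, the resampled lower limit exceeded 0.40 in more than 99.9% of samples. SAP Table 5, which substitutes diameter for area, likewise gives 99.9% power.

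**What to change.** In SAP 3.5 and 3.10.8 and in Tables 15.2.1.2.x:
- Keep the investigator-assessed diameter as the protocol's named endpoint.
- Add the three DAR analyses (maximum, Day 6-8, Day 13-15) on the camera diameter, with the same HL method.
- Summarise IMLD minus SMLD by group at each time point. A constant offset in both groups is only a difference between methods; a difference between groups is the signal of arm-dependent reading. Because Group 1 lesions are expected to be smaller, interpret it with lesion size in mind, since a proportional offset would also differ between groups.
- Describe the camera rows as coming from the perimeter that yields the ITRC-confirmed area, and not as ITRC-confirmed diameters unless the Charter says so.

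The cost is a few extra table rows from data already captured, specified before database lock. Sample size and alpha do not change. The downside for the sponsor is that the camera-based diameter result may be slightly less favourable; if the two readings agree in both groups, the supportive evidence is stronger.
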